7.9. Subgroup Analyses

Type I error will be 0.05 for subgroup analyses. These analyses will be performed after either a successful interim analysis or the final study analysis. Statistical comparisons are performed for exploratory purposes. No alpha level adjustment for multiple comparisons will be made.

AF diagnoses subgroups

To characterize the consistency of the estimated treatment effect across AF diagnoses (paroxysmal or persistent AF) from the primary effectiveness objective, a score test will be performed on the interaction term in a Cox proportional hazards regression with study arm indicator, AF diagnosis, and interaction between study arm and AF diagnosis as factors. Similar subgroup analyses, assessing the interaction

term in a statistical model, will be performed for the secondary objective and ancillary objectives #1, #2, #4, and #5.

The source data for defining AF diagnosis comes from Section C question 1 on the Baseline CRF. If paroxysmal atrial fibrillation is checked, then the subject is in the paroxysmal AF subgroup. If persistent AF is checked, then the subject is in the persistent AF subgroup.

Pulmonary vein isolation ablation subgroups (RF touch-ups or cryoablation only)

Additionally, a subgroup analysis using the same methodology will be performed to characterize the consistency of the estimated treatment effect across patients who received touch-up ablations to complete the electrical isolation of one or more pulmonary veins with an RF catheter versus those whose pulmonary veins were treated only with cryoablation. This subgroup analysis will be performed for the primary effectiveness objective, the secondary objective, and ancillary objectives #1, #2, #4, and #5.

The source data for defining touch-up ablations comes from questions on the Cardiac Cryoablation Procedure CRF and the Energy Applications CRF.

- Determine if a RF catheter was used at all during the procedure from Section D question 1 on the Cardiac Cryoablation Procedure CRF
 - Get the catheter number for each RF catheter used
- Determine which energy applications were done with the RF catheters from the Energy Applications CRF Section A (using the catheter number to match)
- If any of the energy applications using a RF catheter have one of the following locations, the subject is in the RF touch-ups subgroup; otherwise the subject is in the cryoablation only subgroup
 - LSPV, LIPV, LCPV, LMPV, RSPV, RIPV, RCPV, or RMPV

Subgroup methods for primary effectiveness and secondary objective

Kaplan-Meier curves will be used to estimate the rate of chronic treatment success in each subgroup with a 95% confidence interval. The main effects, interaction effects, confidence intervals, and p-values from each Cox proportional hazards regression will be reported using the score test.

Code similar to the following can be used for the Kaplan-Meier curves and estimates:

```
ODS graphics on ;
PROC LIFETEST DATA=survData conftype=loglog;
  By SubGroup;
  Plots = (survival(atrisk = 0 to <end time> by <interval time>)) ;
  STRATA trtGroup;
  TIME time*event(0);
RUN;
ODS graphics off ;
```

Code similar to the following can be used for the Cox proportional hazards model:

```

PROC PHREG DATA = survData;
  CLASS trtGroup subgroup;
  MODEL time*event(0) = trtGroup subgroup trtGroup*subgroup /
  TIES = efron;
  RUN;

```

The subgroup variable designates what subgroup a given subject belongs to:

- AF Diagnosis
 - If AF diagnosis is paroxysmal, then subgroup equals 0
 - If AF diagnosis is persistent, then subgroup equals 1
- Touch-up ablations
 - If a subject does not receive a touch-up ablation, then subgroup equals 0
 - If a subject receives a touch-up ablation, then subgroup equals 1

Subgroup analysis methods for the ancillary objectives are described in their respective sub-sections in Section 7.10.

7.10. Evaluation of Objectives

7.10.1. Primary Safety

The primary safety objective characterizes the rate of safety composite events within each of the two study arms and also characterizes the difference in the rates between study arms.

7.10.1.1. Hypothesis

There is no pre-specified hypothesis for this objective

7.10.1.2. Performance Criteria and Rationale

Given the exploratory nature of a feasibility study, there is no performance requirement for this objective. The rate of safety composite endpoints will be characterized by estimating the rate within each arm and estimating the difference in rates between arms. These event rate estimates will provide critical guidance for designing a possible subsequent pivotal study.

7.10.1.3. Endpoint Definition

The primary safety composite endpoint combines the safety endpoints from current Medtronic hypertension and AF studies and is intended to include serious adverse events associated with either the renal artery denervation or cryoablation procedure.

The endpoint for this objective is a Safety Composite Event. Safety Composite Events are events that are serious, occur within a specified time interval (see Table 11) starting when the subject undergoes the study pulmonary vein isolation procedure and meet the definition in Section 12.3.1. The CEC

adjudication will be used to classify subjects for this endpoint. The adjudication source is the Medtronic Adverse Event CRF, Section C, question 1. The date of Safety Composite Events will come from the Adverse Event CRF.

Table 1. Safety Composite Events and onset intervals

Serious Adverse Event	Onset Interval
Death	1 month
End-stage renal disease	1 month
Significant embolic event	1 month
Renal artery perforation requiring intervention	1 month
Renal artery dissection requiring intervention	1 month
Vascular complications	1 month
Hospitalization for hypertensive crisis	1 month
New renal artery stenosis	6 months
Cardiac damage	1 month
Pulmonary vein stenosis	6 months
Atrio-esophageal fistula	6 months
Arrhythmia	1 month
Persistent phrenic nerve palsy	6 months

Serious Adverse Event Definitions

- Death
- End-stage renal disease defined as two or more eGFR measurements <15mL/min/1.73m² at least 21 days apart and requiring dialysis for one or more of the following: volume management refractory to diuretics, hyperkalemia unmanageable by diet and diuretics, acidosis bicarbonate <18 unmanageable with HCO₃ supplements, or symptoms of uremia, nausea, vomiting.
- Significant embolic event resulting in end-organ damage (e.g. kidney/bowel infarct, lower extremity ulceration or gangrene, stroke or doubling of serum creatinine confirmed by at least two measurements at least 21 days apart). Stroke is defined as a) rapid onset of a focal or global neurological deficit with at least one of the following: change in level of consciousness, hemiplegia, hemiparesis, numbness or sensory loss affecting one side of the body, dysphasia or aphasia, hemianopia, amaurosis fugax, or other neurological signs or symptoms consistent with stroke, b) duration of a focal or global neurological deficit ≥24 h; OR <24h, if therapeutic intervention(s) were performed (e.g. thrombolytic therapy or intracranial angioplasty); OR the neurological deficit results in death, c) no other readily identifiable nonstroke cause for the clinical presentation (e.g., brain tumor, trauma, infection, hypoglycemia, peripheral lesion, pharmacological influence), d) confirmation of the diagnosis by at least one of the following: neurology or neurosurgical specialist, neuroimaging procedure (MR or CT scan or cerebral angiography), lumbar puncture (i.e., spinal fluid analysis diagnostic or intracranial hemorrhage).

- Renal artery perforation requiring intervention
- Renal artery dissection requiring intervention
- Vascular complications (e.g. clinically significant groin hematoma, arteriovenous fistula, pseudoaneurysm, excessive bleeding) requiring surgical repair, interventional procedure, thrombin injection, or blood transfusion (requiring more than 2 units of packed red blood cells within any 24 hour period during the first 7 days post procedure).
- Hospitalization for hypertensive crisis: Hypertensive crisis/emergency is defined as severely elevated blood pressure, usually higher than 180/110 mm Hg, together with progressive or impending target organ damage, requiring in-patient hospitalization and typically admission to the Intensive Care Unit (e.g., with parenteral IV antihypertensive medications), not related to confirmed non-adherence with medication.
- New renal artery stenosis defined as >70%, confirmed by angiography.
- Cardiac damage (due to any cause except pulmonary vein stenosis or atrio-esophageal fistula and including Myocardial Infarction (MI) (the presence of any one of the following criteria: 1-detection of electrocardiogram (ECG) changes indicative of new ischemia (new ST-T changes or new LBBB) which persist for more than one hour; 2-development of new pathological Q waves on an ECG; 3-imaging evidence of new loss of viable myocardium or new regional wall motion abnormality)).
- Pulmonary vein stenosis defined as >75% reduction in diameter of the baseline pulmonary vein area on CT or MRI.
- Atrio-esophageal fistula defined as a connection between the atrium and the lumen of the esophagus. Evidence supporting this diagnosis includes documentation of esophageal erosion combined with evidence of a fistulous connection to the atrium such as air emboli, an embolic event, or direct observation at the time of surgical repair. A CT scan or MRI scan are the most common methods of documentation of an atrial-esophageal fistula.
- Arrhythmia excludes atrial fibrillation and including creation of new arrhythmias and/or worsening of existing arrhythmias.
- Persistent phrenic nerve palsy defined as absent phrenic nerve function as assessed by a sniff test or chest x-ray including inspiration/expiration films. Persistent is defined as lasting 6 months or longer, or lasting until the last known follow-up if the follow-up is less than 6 months.

7.10.1.4. Analysis Methods

For computing the proportion of subjects in each arm that experience safety composite events, Kaplan-Meier methods will be used. Since all components of the safety composite event include events through 30 days and four components include events through 6 months post-procedure, there is the potential for some subjects having incompletely assessed safety composite outcomes should they discontinue study participation prior to 6 months of post-procedure follow-up. Kaplan-Meier estimation uses the time that each subject is free from a safety composite event, defined from the date of procedure (time 0) to the earliest date that an event meeting one of the safety composite event component definitions occurs. For events that are typically confirmed at a clinic visit (e.g. renal artery stenosis confirmed with angiography),

it can be difficult to determine the onset date exactly. Therefore, events whose onset date is equal to a follow-up visit date within the 6-month visit window will be treated as having occurred at 180 days post-procedure. All subjects that are event-free through a completed 6-month follow-up visit within the 6-month visit window will be censored at 180 days. Otherwise, a subject's event-free time will be from the date of procedure to the latest follow-up visit. Treating safety composite event dates and censoring dates that occur at 6-month visits within the 6-month visit window as occurring at exactly 180 days post-procedure prevents not counting them in the Kaplan-Meier 6-month estimate. The log-log transformation will be used to calculate a two-sided 95% confidence interval for the rate of safety composite events within each study arm.

The difference in event rate between arms will be estimated by the difference in Kaplan-Meier estimates at 6 months. A 95% confidence interval for the difference will be constructed by applying the delta method to the log-log transform of the difference in the Kaplan-Meier estimates.

The confidence interval estimates the precision of the estimated difference in event rates between arms for the sample with a 95% confidence level. If the 95% confidence interval for the difference does not contain 0, we can conclude the event rates differ significantly between the Treatment and Control arms at a 5% significance level.

Code similar to the following can be used to obtain estimates in each treatment arm:

```
PROC LIFETEST DATA=survData conftype=loglog;
  STRATA trtGroup;
  TIME time*event(0);
  TEST trtGroup;
RUN;
```

Other code may be needed to analyze the difference in event rates between arms.

Explanation of variables

- trtGroup (treatment group):
 - Equals 1 if subject randomized to the treatment arm
 - Equals 0 if subject randomized to the control arm
- Event
 - Equals 1 if subject experienced a component of the primary safety endpoint during follow-up on or before the 6-month visit
 - Equals 0 if a subject did not experience a component of the primary safety endpoint during follow-up on or before the 6-month visit
- Time (from procedure date to first event or censor in days)
 - If Event = 1

- Determine the earliest date that a component of the primary safety endpoint was experienced for each subject
 - If the earliest event onset date is equal to a follow-up visit date within the 6-month visit window, then Time equals 180 days
 - If the earliest event onset date is prior to the subjects 6-month visit window, then Time equals the earliest date that a component of the primary safety endpoint was experienced minus the date of procedure
- If Event = 0 (censor)
 - and the 6-month follow-up visit was completed within the 6-month visit window, then Time equals 180 days
 - and the 6-month follow-up visit was not completed, then Time equals the date of the latest visit prior to the 6-month visit minus the date of procedure

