#### *12.3.2 Hypothesis*

There is no hypothesis for this objective.

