#### *12.3.4 Rationale for Performance Criteria*

This primary safety endpoint is a composite that combines the safety endpoints from current Medtronic hypertension and AF studies and is intended to include serious adverse events associated with either the renal artery denervation or cryoablation procedure.

The safety composite event rate in the STOP-AF trial was 3.1% with a one-sided upper 95% confidence bound of 6.3%. The safety composite event rate in subjects undergoing renal artery denervation using the first generation Symplicity system (Symplicity Catheter and G2 Generator) in the Symplicity HTN-3 trial 1.4% (one-sided upper 95% confidence bound of 2.9%). If undergoing both pulmonary vein isolation and renal artery denervation procedures at once is as safe as undergoing each procedure separately, then the proportion of patients that would be expected to experience a composite safety event is approximately 4.5% (based on observed rates) to 9.2% (based on upper 95% confidence bounds).

A DMC will periodically review accumulating safety data for the study, including the rate of safety composite events within each study arm and the difference in the rate between study arms.

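### The confidence interval for the primary safety difference does not exist when the difference is zero or negative, and can never include zero when it is positive

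*SAP*

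**What the plan says.** The primary safety objective is to estimate the composite event rate in each arm and the difference between arms. SAP 7.10.1.4 gives the estimator: "The difference in event rate between arms will be estimated by the difference in Kaplan-Meier estimates at 6 months".

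Two interval methods follow. For each arm: "The log-log transformation will be used to calculate a two-sided 95% confidence interval for the rate of safety composite events within each study arm". For the difference, the interval is "constructed by applying the delta method to the log-log transform of the difference in the Kaplan-Meier estimates". Protocol 12.3.5 uses the same words for the difference.

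The SAP, but not the protocol, then adds a decision rule: "If the 95% confidence interval for the difference does not contain 0, we can conclude the event rates differ significantly" between the arms "at a 5% significance level". Protocol 12.3.2 states: "There is no hypothesis for this objective". SAP 7.10.1.1 agrees, and neither document sets a performance requirement.

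Neither document gives a formula for the difference interval, an order of subtraction, or a rule for a zero or negative difference. The SAP's sample code covers only the arm-specific estimates and leaves the code for the difference open.

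**The concern.** The log-log transform suits a single survival probability, which lies between 0 and 1. A difference of two probabilities lies between -1 and 1. With few events expected, zero and negative values are ordinary outcomes, and for these the method gives nothing. For positive values it gives an interval that excludes zero by construction, so the SAP's rule would call any excess, even a single event, a significant difference in safety.

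The difference is an explicit part of a primary objective. Protocol 12.3.3 says the estimates are to guide the design of a possible pivotal study. An interval that is either missing or falsely positive would mislead that design. A replacement method would also have to be chosen after the results by arm were known.

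**Working it through.** **Inputs**

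- Sample size: 70, allocated 1:1, taken as 35 per arm (SAP 5.3 and 6).
- Rates from protocol 12.3.4: cryoablation alone 3.1% (upper bound 6.3%); renal denervation alone 1.4% (upper bound 2.9%).
- The plan's projection for both procedures reproduces as a sum: 3.1 + 1.4 = 4.5% and 6.3 + 2.9 = 9.2%.
- Assumptions: Control has the cryoablation-alone rate; no censoring before day 180, so the Kaplan-Meier estimate is the simple proportion; d is Treatment minus Control.

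**The stated method**

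Let d be the difference and SE its Greenwood standard error. Then g = log(-log d), SE(g) = SE / |d log d|, and the limits are d^exp(+1.96 SE(g)) and d^exp(-1.96 SE(g)).

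- If d ≤ 0, log d is not defined, so g is not defined.
- If 0 < d < 1, a positive power of d always lies strictly between 0 and 1, so neither limit can reach 0.

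Censoring changes SE but neither of these facts. Using log(-log(1-d)) instead fails in the same way.

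**Example: 2/35 Treatment events, 1/35 Control events**

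- d = 0.0571 - 0.0286 = 0.0286; SE = 0.0483.
- |d log d| = 0.0286 × 3.555 = 0.1016; SE(g) = 0.0483 / 0.1016 = 0.475.
- exp(1.96 × 0.475) = 2.54.
- Lower limit: 0.0286^2.54 = 0.00012. Upper limit: 0.0286^(1/2.54) = 0.2465.

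The SAP would call this one-event gap significant.

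**Other outcomes (percentage points)**

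| Events, Treatment / Control | d | As written | Greenwood | Newcombe |
|---|---|---|---|---|
| 2 / 1 | 2.9 | 0.012 to 24.7 | -6.6 to 12.3 | -9.5 to 16.0 |
| 3 / 1 | 5.7 | 0.39 to 22.8 | -5.1 to 16.5 | -7.2 to 19.7 |
| 1 / 1 | 0 | none | -7.8 to 7.8 | -11.9 to 11.9 |
| 1 / 2 | -2.9 | none | -12.3 to 6.6 | -16.0 to 9.5 |
| 0 / 0 | 0 | none | 0 to 0 | -9.9 to 9.9 |

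**How often each failure occurs** (exact enumeration of two independent binomials, n = 35 each)

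| True rates, Treatment / Control | No interval (d ≤ 0) | Interval, always excluding 0 |
|---|---|---|
| 4.5% / 3.1% | 51% | 49% |
| 9.2% / 6.3% | 41% | 59% |
| 3.1% / 3.1% | 65% | 35% |
| 9.2% / 9.2% | 58% | 42% |

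The last two rows give the false-positive rate of the SAP's rule: 35% and 42%, against a stated 5%. If the larger rate is always put first, these become 70.5% and 83.3%. For comparison, over equal true rates of 3.1% to 9.2% the same rule has an error rate of 1.5% to 5.7% with a Greenwood interval and 0.3% to 3.0% with Newcombe.

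**Arms with no events**

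A log-log interval within an arm is also undefined with zero events. At 4.5% and 3.1% the chance of zero events is 0.955^35 = 0.200 in Treatment and 0.969^35 = 0.332 in Control. For at least one arm it is 1 - 0.800 × 0.668 = 46.5%. At 9.2% and 6.3% it is 13.3%.

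**The case against.** **The wording may be loose.** The authors may have meant to transform each arm's estimate and carry the variance back to the probability scale. That gives the ordinary Greenwood interval, which is defined for either sign. With one zero-event arm it is poor but computable; it collapses only when both arms have none, about 0.200 × 0.332 = 6.6% of trials at the lower rates. This is a workable method, and under it the 46.5% is not a rate of outright failure. But neither document states it: the arm-specific transform has its own sentence, and the next one names the difference as the thing transformed. Contrasting the two log-log values directly would compare cumulative hazards, which is not the stated rate difference.

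**The objective is descriptive.** No stopping rule or success criterion uses this interval, and the arm rates, their point estimates and the estimated difference are unaffected. This stands, and it limits the harm to reporting and pivotal design. The SAP nevertheless attaches a 5% conclusion to the interval.

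**A missing interval would be noticed.** True for d ≤ 0. For d > 0 the program returns plausible limits and the failure is silent.

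**A test without a hypothesis is not unusual here.** The SAP also tests its secondary objective and ancillary objective 5 without a stated hypothesis. This is fair: with a valid interval the sentence would be standard, and its conflict with the absence of a hypothesis is a secondary point.

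**The frequencies depend on assumptions.** Neither document fixes the order of subtraction; with Control minus Treatment the undefined share at the lower rates is 74%. The protocol also does not name 3.1% as a planning rate for Control. These points change the size of the problem, not its existence.

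**Conclusion.** The method is wrong as written, and nothing elsewhere in the documents repairs it. No outcome yields a usable interval: at d ≤ 0 none exists, and at d > 0 zero is excluded whatever the data. This is algebra and holds under any censoring or event rate. Only the frequencies rest on the working assumptions of 35 per arm, the protocol's historical rates, no early censoring and Treatment minus Control. The error affects one interval and the conclusion drawn from it, within a primary objective.

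**What to change.** - **Estimate.** State it as the Treatment minus Control difference in 6-month Kaplan-Meier event rates.
- **Interval.** Use square-and-add (Newcombe, also called MOVER). With arm rates p1, p0 and arm limits (l1, u1), (l0, u0), the lower limit is d - √[(p1 - l1)² + (u0 - p0)²] and the upper limit is d + √[(u1 - p1)² + (p0 - l0)²].
- **Arm limits.** For this calculation use Wilson limits in every case, so that the method does not switch on the observed result. Take the effective sample size as p(1 - p) divided by the Greenwood variance or, in an arm with no events, as the number still at risk just before day 180.
- **Within-arm report.** Add the same zero-event rule to the arm-specific log-log interval, which is otherwise undefined in such an arm.
- **Significance sentence.** Delete it. The protocol has no such sentence and sets no hypothesis.

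The cost is a few sentences of wording and a short program; the SAP already expects extra code for the difference. Data, sample size and conduct do not change. Protocol 12.3.5 needs the same correction. Protocol 12.2 and SAP 7.13 require an amendment only for a change to a principal feature, so the SAP can be corrected first and the change justified in the study report. Revising the protocol itself would need the approvals listed in its section 4. The correction should be made before the safety results by arm are analysed.

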7.10.1.5. Datasets Analyzed

The mITT analysis set will be used for this objective.

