## 6.10 Pulmonary vein isolation procedure

Perform the pulmonary vein isolation procedure first using Arctic Front Advance/Arctic Front Advance Pro. Investigator is to perform the procedure according to the procedural steps in this protocol and the Instructions for Use for the Arctic Front Advance/Arctic Front Advance Pro Cardiac Cryoablation System. Appropriate systemic anticoagulation and sedation should be attained at the investigators discretion according to their institutions pre- established procedures/guidelines at the time of the procedure. Current recommendations for anticoagulation are found in the 2012 Expert Consensus Statement on the Ablation of atrial fibrillation.

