### 12.2 General considerations

A modified intention-to-treat analysis will be performed and will serve as the primary analysis for all objectives in this study. The modified intention-to-treat

cohort will include all randomized subjects that undergo a pulmonary vein isolation procedure (i.e. have a cryocatheter inserted). Patients that are randomized, and meet either of the following two conditions will not be included in this cohort:

- exit the study without undergoing a pulmonary vein isolation procedure
- subjects who are randomized to the treatment group and are found not to meet inclusion/exclusion criteria during the renal denervation procedure.

The Statistical Analysis Plan (SAP) will include a comprehensive description of the statistical methods and reports to be included in the final study report. Any change to the data analysis methods described in the CIP will require an amendment only if it changes a principal feature of the protocol. Any other change to the data analysis methods described in the protocol, and the justification for making the change, will be described in the clinical study report.

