#### *12.3.6 Determination of Patients/Data for Analysis*

All randomized subjects in the modified intention-to-treat cohort will be included in the analysis.

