5.6. Data Monitoring Committee

A DMC will periodically review accumulating safety data for the study, including the rate of safety composite events within each study arm and the difference in the rate between study arms (i.e., the Primary Safety Objective).

6. Determination of Sample Size

The overall study sample size is 70 randomized subjects that undergo a pulmonary vein isolation procedure which is the required sample size for the primary effectiveness objective.

Subjects that are enrolled in the study may not go on to be randomized due to a variety of reasons, including elective withdrawal prior to randomization, blood pressure measurements that do not meet study criteria, or renal anatomy that is found to be ineligible upon angiography. Based on the rate of randomization among enrolled subjects in trials with similar screening criteria, up to 245 subjects may need to be enrolled and undergo screening in order to ensure that 70 subjects are randomized.

There will be at least 78% power to test the primary effectiveness objective provided at least 70 subjects undergo randomization and undergo a pulmonary vein isolation procedure. Table 1 below shows the expected incremental power at each analysis. The first and second look correspond to the interim analyses. The third interim look is the final analysis.

Table 1: Power at each stage of the analyses

Look	Patients w/ six month follow-up	Expected Incremental Power of Analysis
1	32	17.6%
2	50	10.1%
3	70	50.9%
Cumulative Power:		78.6%

Subjects who are randomized and meet either of the following two conditions do not count toward the 70 randomized subjects to be used in the mITT set (define below):

- Exit the study without undergoing a pulmonary vein isolation procedure
- Subjects who are randomized to the treatment group and are found not to meet inclusion/exclusion criteria during the renal denervation procedure

The sample size calculation is based on the following assumptions:

- 1:1 randomization
- Constant randomization rate over 16 months
- Last enrolled subject followed through 6 months post-procedure
- 50% chronic treatment success in the Control arm (PVI only) versus 75% in the Treatment arm (equivalent to a hazard ratio of 0.415) through 6 months post-procedure
- Constant hazard ratio over all follow-up
- Constant attrition (dropout) of 5% per 6 months

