7.1.3. Analysis Sets

Cut-off dates will be applied to the study data when creating snapshots for study reporting. The analysis sets will be created from the applicable snapshot (e.g., for final report).

Enrolled

Patients who signed informed consent and met inclusion/exclusion criteria. Deviations and adverse events will be reported for all enrolled subjects. Enrolled subjects will be included in the CONSORT flow diagram.

Randomized

Enrolled subjects who are randomized.

Modified intent-to-treat

A modified intention-to-treat (mITT) analysis will be performed for the primary objectives. The mITT analysis set will include all randomized subjects that undergo a pulmonary vein isolation procedure (i.e. have a cryocatheter inserted). Patients that are randomized, but exit the study without undergoing a pulmonary vein isolation procedure will not be included in the mITT analysis set. Patients that are randomized to the treatment arm, but do not have the renal denervation procedure, will not be included in the mITT analysis set.

This analysis set is used for the following objectives described previously in Section 4:

- Primary safety

- Primary effectiveness
- Ancillary Objective 1
- Ancillary Objective 2
- Ancillary Objective 3
- Ancillary Objective 4
- Ancillary Objective 6

Secondary Objective

All subjects in the mITT cohort (i.e. subjects used for the Primary Effectiveness Objective) that do not undergo an additional pulmonary vein ablation procedure during the 90 day blanked follow-up period will be included the analysis of the secondary objective.

Ancillary Objective 5

The following subjects will be included in the analysis of ancillary objective 5:

- All subjects in the mITT cohort (i.e. subjects used for the Primary Effectiveness Objective) that do not undergo an additional pulmonary vein ablation procedure during the 90 day blanked follow-up period will be included this analysis

AND

- Have not used Class I and III anti-arrhythmic drugs following the blanking period

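### The SAP's mITT set for primary safety drops Treatment subjects who do not reach denervation, so a complication that stops the case leaves the Treatment composite while the same event counts in Control

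*SAP*

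**What the plan says.** Protocol 12.3.6 gives the population for primary safety as: "All randomized subjects in the modified intention-to-treat cohort will be included in the analysis". SAP 7.10.1.5 agrees: "The mITT analysis set will be used for this objective". The two documents define that set differently.

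- **SAP 7.1.3.** Randomized subjects enter once a cryocatheter is inserted. One group is then taken out: "Patients that are randomized to the treatment arm, but do not have the renal denervation procedure, will not be included in the mITT" analysis set. No reason is required, and nothing similar applies to Control.
- **Protocol 12.2.** Besides subjects who never have PVI, it excludes only "subjects who are randomized to the treatment group and are found not to meet inclusion/exclusion criteria during the renal denervation procedure".
- **SAP section 6.** It repeats the narrower rule when it counts the 70 subjects for mITT: "Subjects who are randomized to the treatment group and are found not to meet inclusion/exclusion criteria during the renal denervation procedure".

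SAP 7.13 says that the SAP's own analysis sets will be used for the final report, so the 7.1.3 wording governs. It discusses another population discrepancy with the protocol, but not this one.

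On sequence, protocol 6.10 says: "Perform the pulmonary vein isolation procedure first using Arctic Front Advance/Arctic Front Advance Pro". Renal angiography (6.12) and denervation (6.13) follow, in Treatment only. Under protocol 12.3 the safety window starts at PVI. Table 11 lists cardiac damage, significant embolic events, vascular complications, and renal artery perforation and dissection.

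**The concern.** Membership of the safety set is decided after randomization, in one arm only, and can be decided by the event being measured. Suppose that a serious cardiac or embolic event occurs during PVI and the operator stops. In Control the subject stays in and the event counts. In Treatment the subject has no denervation, so SAP 7.1.3 removes both subject and event. An injury at the renal angiogram that ends the case before denervation is lost in the same way.

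The composite rate in each arm and the difference are the whole output of the primary safety objective. Protocol 12.3.3 says that they will guide a possible pivotal study, and the DMC reviews both. SAP 7.10.1.4 also reads a 95% interval that excludes zero as a significant difference between arms. A set that can lose Treatment events but not the matching Control events makes the added procedure look safer than it is.

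**Working it through.** **Inputs.** Protocol 12.3.4 gives a composite rate of 3.1% for cryoablation (upper bound 6.3%) and 1.4% for denervation (upper bound 2.9%). Protocol 12.1 and 12.4.6 give 70 subjects at 1:1, so about 35 per arm. The documents do not give f, the share of PVI composite events that stop the case before denervation. It is an assumption here, shown as a range.

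**The plan's own figure.** 3.1% + 1.4% = 4.5% and 6.3% + 2.9% = 9.2%, as stated in 12.3.4. Treating the two risks as independent gives 1 - (0.969 × 0.986) = 4.46% and 1 - (0.937 × 0.971) = 9.02%.

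**All subjects with a cryocatheter inserted.** Let pc be the PVI event rate and pr the denervation event rate. The Treatment rate is pc + (1 - pc) × pr = 0.031 + 0.969 × 0.014 = 4.46%, against 3.1% in Control. The difference is +1.36 points and does not depend on f.

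**SAP 7.1.3 set.** A share f of the PVI events leaves both numerator and denominator:

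Treatment rate = [pc(1 - f) + (1 - pc)pr] / (1 - pc × f)

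At f = 0.25: (0.02325 + 0.01357) / 0.99225 = 3.71%. At f = 0.5: (0.0155 + 0.01357) / 0.9845 = 2.95%.

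| f (assumed) | Treatment, observed rates | Minus Control (3.1%) | Treatment, upper bounds | Minus Control (6.3%) |
|---|---|---|---|---|
| 0 | 4.46% | +1.4 points | 9.02% | +2.7 points |
| 0.25 | 3.71% | +0.6 | 7.56% | +1.3 |
| 0.5 | 2.95% | about -0.15 | 6.06% | about -0.2 |

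Setting the formula equal to pc gives f = pr/pc, so the expected difference crosses zero at 0.014/0.031 = 0.45.

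The model leaves the whole 1.4% with subjects who stay in the set. It therefore does not include angiogram injuries lost in the same way.

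**In counts.** The expected number of PVI composite events per arm is 35 × 0.031 = 1.1, and the chance of at least one is 1 - 0.969^35 = 67%. The expected number of subjects removed is 35 × 0.031 × 0.25 = 0.27 at f = 0.25. If one of two Treatment subjects with an event is removed, 2/35 (5.7%) becomes 1/34 (2.9%).

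**The same case under each wording.** A Treatment subject has a serious cardiac event during PVI and the case stops:

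- SAP 7.1.3: no denervation, so the subject and event are excluded.
- Protocol 12.2 and SAP section 6: not found ineligible during denervation, so the subject and event are included.

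**The case against.** Several points on the other side have force.

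- **The effect comes from one wording.** A reader might infer that the problem stays the same whichever mITT definition is adopted. It does not. Under protocol 12.2 and SAP section 6, a subject stopped by a complication stays in. What remains is the one-sided removal of Treatment subjects found ineligible after PVI and angiography. CT screening before randomization should keep that group small, and the direction of bias is not established. Subjects who had PVI but no denervation have an expected rate of about 3.1%, against 4.5% in those who had both. If 10% were ineligible (assumed), their removal would raise the Treatment rate from 0.9 × 4.5% + 0.1 × 3.1% = 4.36% to 4.5%. This stands.
- **High f is implausible.** A reader might infer that the whole expected excess disappears, or that all PVI events are lost. Pulmonary vein stenosis, atrio-esophageal fistula, and later deaths or arrhythmias arise after the case and cannot stop it. The documents do not break down the 3.1%, so nothing supports f = 0.5 in particular. This stands.
- **Perforation and dissection are only partly exposed.** SAP 7.1.3 does not say whether a denervation that was started and then stopped counts as having the procedure. Only injuries in the angiogram phase are clearly affected.
- **The events remain visible.** SAP 7.11 reports all adverse events in enrolled subjects, and SAP 7.1.1 requires the reasons for removal from the primary analysis set. This mitigates the loss but does not cure it: the example table in 7.11 is not split by arm and gives no composite rate.
- **There is no safety hypothesis or performance requirement, and precision is low.** The exact 95% interval for 1/34 is about 0.1% to 15.3%. This lowers the severity. It does not justify an avoidable bias in the estimate.

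Blinding until after PVI protects how PVI is performed, but does not prevent a later exclusion.

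**Conclusion.** The concern holds on the governing SAP text. The 7.1.3 set, used for primary safety, allows a one-sided, outcome-dependent exclusion that biases the Treatment composite rate and the between-arm difference downward. At the protocol's observed rates, the expected difference falls from +1.4 points to +0.6 if a quarter of PVI composite events stop the case, and to about zero if nearly half do. These figures rest on an assumed f and on independent risks for the two procedures. The lower end of the range is the more credible.

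The documents do not support saying that the expected excess will vanish, or that protocol 12.2 carries the same bias. The effect is on estimation in an exploratory objective; no pass/fail decision turns on it. Should-fix.

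**What to change.** - In SAP 7.10.1.5 and protocol 12.3.6, define the primary safety population as all randomized subjects with a cryocatheter inserted, analysed by randomized arm, whether or not denervation was done or anatomy was later found ineligible. Keep the mITT result as a supportive analysis.
- Make the matching edits where both documents assign mITT to this objective (protocol 12.2 and the list in SAP 7.1.3).
- Reconcile the mITT exclusion in SAP 7.1.3 with protocol 12.2 and SAP section 6, and state how a denervation that was started and then stopped is classified.

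The cost is wording in both documents and one extra run. No new data are needed: protocol 6.24 already asks centers to keep following every randomized subject. A subject who exits early for ineligibility would be censored under the planned Kaplan-Meier method. The Treatment safety rate may look slightly less favourable.
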